6.9 Management of Adverse Events of Interest

6.9.1 Adverse Drug Reactions Requiring M3814 Treatment Discontinuation or Modifications

Part A and Part FE (M3814 + Avelumab)

There is no dose reduction allowed for M3814 or avelumab during the DLT period or the FE Assessment Period. The study intervention can only be discontinued due to toxicity. Details on criteria for discontinuation of study interventions are in Section 7.1.

After the DLT and the FE Assessment Period, if not tolerated, treatment with M3814 may be interrupted, modified or stopped at the Investigator's discretion.

Where a SAE (Grade \geq 3) is believed to be due to M3814, M3814 will be withheld until the SAE has resolved to Grade \leq 2. On subsequent cases of the same SAE, permanent dose reductions in 50 mg steps must be done.

In case of a nonserious AE Grade 3, assessed by Investigators as related to M3814, a dose reduction should be considered.

In the case of participants vomits within 1 hour of M3814 dose, please see Section 6.6.5.4.

If M3814 50 mg BID is not tolerated, M3814 will be stopped. Any change from dosing schedule, dose interruptions, or dose reductions should be recorded in the eCRF.

If avelumab treatment is discontinued while M3814 treatment is ongoing, M3814 treatment could be continued if the Investigator believes the participant is experiencing clinical benefit from M3814 treatment.

Part B (M3814 + Radiotherapy + Avelumab)

The formal criteria for M3814 and RT dose modification are presented in Table 15.

Early and late toxicities related to RT and/or M3814 will be managed according to the local institute's guidelines.

Table 15 Dose Modifications for M3814 and Radiotherapy During Part B of the Study

Toxicity	Dose Modifications ^a		
	M3814 ^b	Radiotherapy ^c	
Toxicities in Radiation Field Grade ≥ 3 • Mucositis • Radiation dermatitis	Temporarily interrupt treatment. Resume treatment once severity resolves to Grade ≤ 2	Temporarily interrupt treatment. Resume treatment once severity resolves to Grade ≤ 2	
 Systemic Toxicities Hematologic Toxicities: Any Grade ≥ 4 toxicity, excluding: Grade 4 neutropenia lasting for ≤ 5 days and not associated with fever Isolated Grade 4 lymphocytopenia without clinical correlate 	Temporarily interrupt treatment. Resume treatment (at the same dose) once severity resolves to Grade ≤ 1 or Baseline. In case of a second recurrence, permanently discontinue study intervention.	No action to be taken.	
 Febrile neutropenia Grade 3 thrombocytopenia with medically concerning bleeding 			
 Systemic Toxicities Nonhematologic Toxicities Any Grade ≥ 3 toxicity, excluding: Diarrhea (≤ 3 days duration) following adequate and optimal therapy Nausea and vomiting (≤ 3 days duration) with adequate and optimal therapy Fatigue or headache (≤ 7 days duration) following initiation of adequate supportive care Any other single laboratory values outside of the normal range that have no clinical significance, and that resolve to Grade ≤ 2 with adequate measures within 7 days. 	Temporarily interrupt treatment. Resume treatment (at the same dose) once severity resolves to Grade ≤ 1 or Baseline. In case of a second recurrence, permanently discontinue study intervention. In case of Grade ≥ 3 liver enzyme values, the participant must be monitored at least every 4 days until recovery to Grade ≤ 2.	No action to be taken.	

Toxicity	Dose Modifications ^a	
	M3814 ^b	Radiotherapy
 Treatment-related hepatocellular injury for more than 3 days, such as Grade ≥ 3 ALT or AST with or without elevation of serum total bilirubin to > 2 × ULN, without initial findings of cholestasis (elevated serum alkaline phosphatase) or other apparent clinical causality. 		

AE=adverse event, ALT=alanine aminotransferase; AST=aspartate aminotransferase; CTCAE=Common Terminology Criteria for Adverse Events, RT=radiotherapy, ULN=upper limit of normal. Severity of AEs will be graded using the CTCAE (v 5.0) toxicity grades.

- a Upon the Investigator decision and once discussed with the Sponsor.
- b As all treatments with M3814 will be given in combination with RT, an interruption in the administration of RT would lead to an interruption in treatment with M3814.
- c A maximum RT delay of up to and including 7 days in total is allowed within the complete treatment period. If RT and M3814 treatment have to be delayed by more than 7 days, the participant must be discontinued from M3814 (unless the participant derives a clinical benefit from the study intervention).

Within Part B of this study, a maximum delay of M3814 and/or RT up to and including 7 days in total is allowed within the complete treatment period. If RT and M3814 treatment have to be delayed by more than 7 days, the participant must be discontinued from study intervention unless the Investigator feels that the participant continues to achieve clinical benefit by continuing avelumab according to the study schedule, in this case the participant should be replaced for DLT assessment but could remain on the study and continue to receive monitoring according to the Schedule of Activities (Section 1.3).

If 50 mg QD is not tolerated, M3814 will be stopped. Any change from dosing schedule, dose interruptions, or dose reductions should be recorded in the eCRF.

6.9.2 Adverse Drug Reactions Requiring Avelumab Treatment Discontinuation or Modifications

Treatment with avelumab should be permanently discontinued, if any of the following ADRs occurs:

- Any Grade 4 ADRs:
 - Permanently discontinue avelumab except for laboratory values out of normal range that do not have any clinical correlate.
- Any Grade 3 ADRs:
 - Withhold avelumab except for laboratory values out of normal range that do not have any clinical correlate.
 - Permanently discontinue avelumab if toxicity does not resolve to Grade ≤ 1 or Baseline within 12 weeks of last administration or if the same Grade 3 toxicity recurs (consider consult with the Medical Monitor before permanently discontinuing the treatment).

If dosing is delayed more than 4 weeks, treatment may be resumed after consultation with the study Medical Monitor. Any delay in dosing in excess of 12 weeks is not permitted.

Infusion-related reactions and irAEs should be handled according to guidelines in Section 6.9.2.1.

6.9.2.1 Management of Infusion-Related Reactions

To mitigate infusion-related reactions associated with avelumab, participants have to be premedicated with an antihistamine and with paracetamol (acetaminophen) prior to the first 4 infusions of avelumab. Premedication should be administered for subsequent avelumab doses based upon clinical judgment and the presence/severity of prior infusion reactions.

Management of symptoms should follow the guidelines shown in Table 16.

Table 16 Treatment Modification for Symptoms of Infusion-related Reactions
Associated with Avelumab

Mild transient reaction; infusion interruption not	Decrease the avelumab infusion rate by 50%
 Mild transient reaction: infusion interruption not 	 Decrease the avelumab infusion rate by 50%
indicated; intervention not indicated.	and monitor closely for any worsening.
rade 2 – moderate	
 Therapy or infusion interruption indicated but responds promptly to symptomatic treatment (for example, antihistamines, NSAIDs, narcotics, IV fluids); prophylactic medications indicated for ≤ 24 hours. 	 Temporarily discontinue avelumab infusion. Resume infusion at 50% of previous rate once infusion-related reaction has resolved or decreased to at least Grade 1 in severity and monitor closely for any worsening.
rade 3 or Grade 4 – severe or life-threatening	
Grade 3: Prolonged (for example, not rapidly responsive to symptomatic medication and/or brief interruption of infusion); recurrence of symptoms following initial improvement; hospitalization indicated for clinical sequelae. Grade 4: Life threatening consequences:	 Stop the avelumab infusion immediately and disconnect infusion tubing from the participan Participants have to be withdrawn immediatel from avelumab treatment and must not receiv any further avelumab treatment.
 Grade 4: Life-threatening consequences; urgent intervention indicated. 	

IV=intravenous, NCI-CTCAE=National Cancer Institute-Common Terminology Criteria for Adverse Event, NSAIDs=nonsteroidal anti-inflammatory drugs.

6.9.2.2 Immune-Related Adverse Events

Since inhibition of PD-L1 stimulates the immune system, irAEs may occur. Treatment of irAEs is mainly dependent upon severity (NCI-CTCAE grade):

- Grade 1 to 2: treat symptomatically or with moderate dose steroids, more frequent monitoring
- Grade 1 to 2 (persistent): manage similar to high grade AE (Grade 3 to 4)
- Grade 3 to 4: treat with high dose corticosteroids

Treatment of irAEs should follow guidelines as shown in Table 17.

[figure not shown]

Table 17 Management of Immune-Related Adverse Events

Gastrointestinal irAEs			
Severity of Diarrhea/Colitis	Initial Management	Follow-up Management	
Grade 1 Diarrhea: < 4 stools/day over Baseline Colitis: asymptomatic	Continue avelumab therapy Symptomatic treatment (e.g. loperamide)	Close monitoring for worsening symptoms Educate participant to report worsening immediately If worsens: Treat as Grade 2, 3 or 4.	
Grade 2 Diarrhea: 4 to 6 stools per day over Baseline; IV fluids indicated < 24 hours; not interfering with ADL Colitis: abdominal pain; blood in stool	Withhold avelumab therapy Symptomatic treatment	If improves to Grade ≤ 1: Resume avelumab therapy If persists > 5 to 7 days or recurs: Treat as Grade 3 or 4.	
Grade 3 to 4 Diarrhea (Grade 3): ≥ 7 stools per day over Baseline; incontinence; IV fluids ≥ 24 h; interfering with ADL Colitis (Grade 3): severe abdominal pain, medical intervention indicated, peritoneal signs Grade 4: life-threatening, perforation	Withhold avelumab for Grade 3. Permanently discontinue avelumab for Grade 4 or recurrent Grade 3. 1.0 to 2.0 mg/kg/day prednisone IV or equivalent Add prophylactic antibiotics for opportunistic infections Consider lower endoscopy	If improves: Continue steroids until Grade ≤ 1, then taper over at least 1 month; resume avelumab therapy following steroids taper (for initial Grade 3). If worsens, persists > 3 to 5 days, or recurs after improvement: Add infliximab 5 mg/kg (if no contraindication). Note: infliximab should not be used in cases of perforation or sepsis.	
	Dermatological irAEs		
Grade of Rash	Initial Management	Follow-up Management	
Grade 1 to 2 Covering ≤ 30% body surface area	Continue avelumab therapy. Symptomatic therapy (for example, antihistamines, topical steroids)	If Grade 2 persists > 1 to 2 weeks or recurs: Withhold avelumab therapy Consider skin biopsy Consider 0.5-1.0 mg/kg/day prednisone or equivalent. Once improving, taper steroids over at least 1 month, consider prophylactic antibiotics for opportunistic infections, and resume avelumab therapy following steroids taper. If worsens: Treat as Grade 3 to 4.	

Grade 3 to 4 Grade 3: Covering > 30% body surface area; Grade 4: Life-threatening consequences	Withhold avelumab for Grade 3. Permanently discontinue for Grade 4 or recurrent Grade 3. Consider skin biopsy Dermatology consult 1.0 to 2.0 mg/kg/day prednisone or equivalent Add prophylactic antibiotics for opportunistic infections	If improves to Grade ≤ 1: Taper steroids over at least 1 month; resume avelumab therapy following steroids taper (for initial Grade 3).
	Pulmonary irAEs	
Grade of Pneumonitis	Initial Management	Follow-up Management
Grade 1 Radiographic changes only	Consider withholding avelumab therapy Monitor for symptoms every 2 to 3 days Consider Pulmonary and Infectious Disease consults	Reassess at least every 3 weeks If worsens: Treat as Grade 2 or Grade 3 to 4.
Grade 2 Mild to moderate new symptoms	Withhold avelumab therapy Pulmonary and Infectious Disease consults Monitor symptoms daily; consider hospitalization 1.0 to 2.0 mg/kg/day prednisone or equivalent Add prophylactic antibiotics for opportunistic infections Consider bronchoscopy, lung biopsy	Reassess every 1 to 3 days If improves: When symptoms return to Grade ≤ 1, taper steroids over at least 1 month, and then resume avelumab therapy following steroids taper If not improving after 2 weeks or worsening or for recurrent Grade 2: Treat as Grade 3 to 4.
Grade 3 to 4 Grade 3: Severe new symptoms; New/worsening hypoxia; Grade 4: Life-threatening	Permanently discontinue avelumab therapy. Hospitalize. Pulmonary and Infectious Disease consults. 1.0 to 2.0 mg/kg/day prednisone or equivalent Add prophylactic antibiotics for opportunistic infections Consider bronchoscopy, lung biopsy	If improves to Grade ≤ 1: Taper steroids over at least 1 month If not improving after 48 hours or worsening: Add additional immunosuppression (for example, infliximab, cyclophosphamide, IV immunoglobulin, or mycophenolate mofetil).
	Hepatic irAEs	
Grade of Liver Test Elevation	Initial Management	Follow-up Management

New onset of cardiac signs or symptoms and/or new laboratory cardiac biomarker elevations (e.g. troponin, CK-MB, BNP) or cardiac imaging abnormalities suggestive of myocarditis.	Withhold avelumab therapy. Hospitalize. In the presence of life-threatening cardiac decompensation, consider transfer to a facility experienced in advanced heart failure and arrhythmia management. Cardiology consult to establish etiology and rule out immune-mediated myocarditis. Guideline based supportive treatment as per cardiology consult. a Consider myocardial biopsy if recommended per cardiology consult.	If symptoms improve and immune-mediated etiology is ruled out, restart avelumab therapy. If symptoms do not improve/worsen, viral myocarditis is excluded, and immune-mediated etiology is suspected or confirmed following cardiology consult, manage as immune-mediated myocarditis.
Immune-mediated myocarditis	Permanently discontinue avelumab. Guideline based supportive treatment as appropriate as per cardiology consult.a 1.0 to 2.0 mg/kg/day prednisone or equivalent Add prophylactic antibiotics for opportunistic infections.	Once improving, taper steroids over at least 1 month. If no improvement or worsening, consider additional immunosuppressants (e.g. azathioprine, cyclosporine A).
^a Local guidelines, or e.g. ESC or AF PPD AHA guidelines website: PPD	IA guidelines	
	Endocrine irAEs	
Endocrine Disorder	Initial Management	Follow-up Management
Grade 1 or Grade 2	Continue avelumab therapy	Continue hormone

Endocrine irAEs			
Endocrine Disorder	Initial Management	Follow-up Management	
Grade 1 or Grade 2 endocrinopathies (hypothyroidism, hyperthyroidism, adrenal insufficiency, type I diabetes mellitus)	Continue avelumab therapy Endocrinology consult if needed Start thyroid hormone replacement therapy (for hypothyroidism), antithyroid treatment (for hyperthyroidism), corticosteroids (for adrenal insufficiency) or insulin (for Type I diabetes mellitus) as appropriate. Rule out secondary endocrinopathies	Continue hormone replacement/suppression and monitoring of endocrine function as appropriate.	
	(i.e. hypopituitarism/hypophysitis)		

Phase I Study of Avelumab-M3814 Combinations

Grade 3 or Grade 4 endocrinopathies (hypothyroidism, hyperthyroidism, adrenal insufficiency, type I diabetes mellitus)	Withhold avelumab therapy Consider hospitalization Endocrinology consult Start thyroid hormone replacement therapy (for hypothyroidism), antithyroid treatment (for hyperthyroidism), corticosteroids (for adrenal insufficiency) or insulin (for type I diabetes mellitus) as appropriate. Rule out secondary endocrinopathies (i.e. hypopituitarism/hypophysitis)	Resume avelumab once symptoms and/or laboratory tests improve to Grade ≤ 1 (with or without hormone replacement/suppression). Continue hormone replacement/suppression and monitoring of endocrine function as appropriate.
Hypopituitarism/Hypophysitis (secondary endocrinopathies)	If secondary thyroid and/or adrenal insufficiency is confirmed (i.e. subnormal serum thyroxine with inappropriately low thyroidstimulating hormone and/or low serum cortisol with inappropriately low adrenocorticotropic hormone) Refer to endocrinologist for dynamic testing as indicated and measurement of other hormones (FSH, LH, GH/IGF-1, PRL, testosterone in men, estrogens in women) Hormone replacement/suppressive therapy as appropriate Perform pituitary MRI and visual field examination as indicated If hypophysitis confirmed: Continue avelumab if mild symptoms with normal MRI. Repeat the MRI in 1 month. Withhold avelumab if moderate, severe or life-threatening symptoms of hypophysitis and/or abnormal MRI. Consider hospitalization. Initiate corticosteroids (1 to 2 mg/kg/day prednisone or equivalent) followed by corticosteroids taper during at least 1 month. Add prophylactic antibiotics for opportunistic infections.	Resume avelumab once symptoms and hormone tests improve to Grade ≤ 1 (with or without hormone replacement). In addition, for hypophysitis with abnormal MRI, resume avelumab only once shrinkage of the pituitary gland on MRI/CT scan is documented. Continue hormone replacement/suppression therapy as appropriate.

Other irAEs (not described above)			
Grade of other irAEs	Initial Management	Follow-up Management	
Grade 2 or Grade 3 clinical signs or symptoms suggestive of a potential irAE	Withhold avelumab therapy pending clinical investigation	If irAE is ruled out, manage as appropriate according to the diagnosis and consider restarting avelumab therapy If irAE is confirmed, treat as Grade 2 or 3 irAE.	
Grade 2 irAE or first occurrence of Grade 3 irAE	Withhold avelumab therapy 1.0 to 2.0 mg/kg/day prednisone or equivalent Add prophylactic antibiotics for opportunistic infections Specialty consult as appropriate	If improves to Grade ≤ 1: Taper steroids over at least 1 month and resume avelumab therapy following steroids taper.	
Recurrence of same Grade 3 irAEs	Permanently discontinue avelumab therapy 1.0 to 2.0 mg/kg/day prednisone or equivalent Add prophylactic antibiotics for opportunistic infections Specialty consult as appropriate	If improves to Grade ≤ 1: Taper steroids over at least 1 month.	
Grade 4	Permanently discontinue avelumab therapy 1.0 to 2.0 mg/kg/day prednisone or equivalent and/or other immunosuppressant as needed Add prophylactic antibiotics for opportunistic infections Specialty consult.	If improves to Grade ≤ 1: Taper steroids over at least 1 month	
Requirement for 10 mg per day or greater prednisone or equivalent for more than 12 weeks for reasons other than hormonal replacement for adrenal insufficiency	Permanently discontinue avelumab therapy Specialty consult		
Persistent Grade 2 or 3 irAE lasting 12 weeks or longer			

ADL=activities of daily living, AHA=American Heart Association, ALT=alanine aminotransferase, AST=aspartate aminotransferase, BNP=B-type natriuretic peptide, CK-MB=creatine kinase MB, CT= computed tomography, ESC=European Society of Cardiology, FSH=follicle-stimulating hormone, GH=growth hormone, IGF-1=insulin-like growth factor 1, irAE=immune-related adverse event, IV=intravenous, LH=luteinizing hormone, MRI=magnetic resonance imaging, NCI-CTCAE=National Cancer Institute-Common Terminology Criteria for Adverse Events, PRL=prolactin, T4=thyroxine, TSH=thyroid-stimulating hormone, ULN=upper limit of normal.

6.9.3 Radiotherapy

6.9.3.1 Management of Adverse Drug Reactions for Radiotherapy

Toxicities related to RT will be managed according to the local institute's guidelines. More details on the treatment of most frequent radiation AEs are outlined in Appendix 8.

7 Discontinuation of Study Intervention and Participant Discontinuation/Withdrawal

7.1 Discontinuation of Study Intervention

The participant must be withdrawn from study intervention(s) in the event of any of the following:

- Participants meeting the definition of confirmed PD while on treatment based on RECIST v 1.1.
 (Note: participants who experience confirmed PD may continue treatment with study drugs in
 the conditions described in Section 6.6.7). Such participants will be withdrawn from the
 treatment if any other criteria for withdrawal are met or if alternative treatment options are
 available and indicated.
- Occurrence of an exclusion criterion which is clinically relevant and affects the participant's safety, if discontinuation is considered necessary by the Investigator and/or Sponsor.
- Therapeutic failure requiring urgent additional therapeutic intervention (if applicable, see allowable local treatment in Section 6.5).
- Significant clinical deterioration (clinical progression), defined as new symptoms that are deemed by the Investigator to be clinically significant or significant worsening of existing symptoms.
- Occurrence of AEs that require discontinuation of study intervention as judged by the Investigator and/or the participant (if applicable).
- Occurrence of any clinically significant and study-intervention-related Grade ≥ 3 nonhematologic or Grade ≥ 4 hematologic ADRs or as described in Section 6.6.3.
- Use of a nonpermitted concomitant drug, as defined in Section 6.5.3, where the predefined consequence is withdrawal from the study intervention(s).
- New approved therapy that is considered more suitable according to the Principal Investigator.
- Noncompliance as defined in Section 6.4 only if the benefit-risk assessment for continuation of study interventions is negative in the individual case as per Investigator judgment.
- Request of the participant to discontinue study intervention. Participants will be followed on the study according to schedule except in case of withdrawal of consent.
- If the benefit-risk assessment for continuation of treatment is negative according to Investigator assessment.
- Adverse drug reactions that cause RT delays of > 7 days or discontinuation of RT (for Part B only).
- Pregnancy.

Participants who come off treatment must be followed on study including completion of all study assessments, most importantly tumor assessments until confirmed disease progression, and resolution of toxicity or discontinuation of the study.

Participants may be withdrawn from one of the study interventions, e.g. in case of intolerance or toxicity clearly attributable to a specific study intervention. Participants who are partially withdrawn from one of the study interventions and continue to achieve clinical benefit may continue with the other study interventions according to schedule until the protocol-defined criteria for discontinuation from treatment are met.

If avelumab treatment is discontinued while M3814 treatment is ongoing, M3814 treatment could be continued if the Investigator believes the participant is experiencing clinical benefit from M3814 treatment.

The Schedule of Activities specifies the data to collect at study intervention discontinuation and follow-up, and any additional evaluations that need to be completed.

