- Mucositis (mucosal inflammation), including oral mucositis (stomatitis) or esophagitis of Grade ≥ 3 lasting for ≤ 4 weeks after completion of the study treatments
- Stomatitis associated toxicities (e.g., swallowing dysfunction [odynophagia, dysphagia], decreased appetite, or weight loss due to difficulty or painful swallowing) of Grade ≥ 3 lasting for ≤ 4 weeks after completion of the study treatments
- Radiation dermatitis and associated toxicities of Grade ≥ 3 lasting for ≤ 4 weeks after completion of the study treatments
- For participants suffering from squamous cell carcinoma of head and neck and who receive RT in the head and neck region: the duration of feeding tube (FT) use (nasogastric tube, percutaneous endoscopic gastrostomy) should not define the severity of the toxicity (e.g., severe swallowing dysfunction, nausea, vomiting). A careful evaluation of the participant's symptoms by the Investigator at each visit is required in order to identify participants who are FT dependent (e.g., participants who refuse/avoid swallowing, etc).

At any time during the study, the SMC may identify as a DLT any adverse drug reactions (ADR) in participants treated with M3814 in combination with avelumab (Part A) and with avelumab and RT including in-field late radiation toxicities (Part B).

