9.1 Statistical Hypotheses

No formal statistical hypothesis will be tested, as the study is designed to be exploratory.

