- The participant will not be eligible if >10% of the total esophagus volume is estimated to receive more than 15 Gy (50% of the prescribed RT dose).

In general, acute RIE occurs typically 2 weeks after treatment begins and lasts until 4 weeks after treatment concludes, with progressively worsening odynophagia, nausea, dysphagia, and, if ineffectively managed, anorexia (Murro 2015; Baker 2016). Late RIE occurs more than 3 months after RT ends, with an average time from treatment to symptom onset of 6 months.

Radiation-induced esophagitis does not constitute a reason to interrupt or delay RT or the study interventions provided oral intake is sufficient to maintain hydration.

Radiation-induced esophagitis is treated symptomatically. Mild to moderate odynophagia is managed with topical analgesics such as oral viscous lidocaine (Berkey 2010; Sasso 2001). Treatment with nonsteroidal anti-inflammatory agents has been proposed. Reflux frequently associated with RIE can be treated with proton pump inhibitors or H2 receptor blocker and dietary modifications. Prophylactic antifungal agents are recommended due to a high incidence of thrush and candida esophagitis.

Participants should also be strongly advised to avoid alcoholic, acidic, or spicy foods or beverages during RT.

Radiation-Induced Lung Toxicity (RILT)

Common radiation lung toxicity includes radiation pneumonitis and fibrosis and pleural effusion.

Traditionally, RILT, which includes clinical radiation pneumonitis and clinical fibrosis should only be diagnosed after exclusion of infection, tumor progression, and other etiology for the clinical symptoms.

Several studies have evaluated the use of various drug therapies to mitigate radiation pneumonitis, but there are none outside of steroid therapy that are in routine use (Abratt 2002). Minimizing the volume of irradiated lung is particularly important as several studies have correlated dose and/or volume effects of RT with the risk of pneumonitis (De Ruysscher 2019).

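### Section 7.1 mandates withdrawal for related Grade ≥ 3 nonhematologic (or Grade ≥ 4 hematologic) reactions that Section 6.9, Table 15 and Appendix 8 manage by holding, resuming or continuing; in some Part B cases the passage followed decides DLT evaluability or status

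*Protocol*

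**What the plan says.** Section 7.1 of the protocol applies to all three parts. It opens with "The participant must be withdrawn from study intervention(s) in the event of any of the following", and one bullet is "Occurrence of any clinically significant and study-intervention-related Grade ≥ 3 nonhematologic or Grade ≥ 4 hematologic ADRs". That bullet closes with an alternative limb pointing to Section 6.6.3.

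Other passages instruct sites on events that meet this description:

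- **Table 15, in-field toxicity (Part B).** For Grade ≥ 3 mucositis or radiation dermatitis, M3814 and RT are both interrupted and both resumed at Grade ≤ 2.
- **Table 15, systemic toxicity (Part B).** M3814 is interrupted, then: "Resume treatment (at the same dose) once severity resolves to Grade ≤ 1 or Baseline". A permanent stop comes at a second recurrence. RT continues unchanged.
- **Section 6.9.1 (Parts A and FE).** For a Grade ≥ 3 SAE attributed to M3814, "M3814 will be withheld until the SAE has resolved to Grade" ≤ 2, with stepwise reduction if the same SAE returns. For a nonserious related Grade 3 AE, a dose reduction is to be considered.
- **Section 6.9.2.** At Grade 3: "Withhold avelumab except for laboratory values out of normal range that do not have any clinical correlate". The stop becomes permanent only if the event fails to resolve within 12 weeks or recurs. Grade 4 leads to permanent discontinuation, which agrees with Section 7.1.
- **Appendix 8.** "Radiation-induced esophagitis does not constitute a reason to interrupt or delay RT or the study interventions provided oral intake is sufficient to maintain hydration". No grade limit is attached.

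Section 7.1 also lets a participant leave one intervention and stay on the others. Section 7.1.1 permits rechallenge after an AE-related discontinuation, as set out in Section 6.9.

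Section 6.6.3 counts as a DLT any related toxicity that takes M3814 below 80% in the DLT period. It then lists exceptions that are not DLTs. For Part B these include "Mucositis (mucosal inflammation), including oral mucositis (stomatitis) or esophagitis of Grade ≥ 3", if it lasts no more than 4 weeks after treatment ends.

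**The concern.** A site facing one related Grade 3 nonhematologic event finds a mandatory withdrawal in one section and a hold, or no action, in another. For Grade ≥ 3 esophagitis in the radiation field there may be three answers: withdraw (Section 7.1), interrupt and resume (Table 15, if esophagitis falls under mucositis as Section 6.6.3 groups it), or carry on (Appendix 8). This is the radiation risk for which the protocol adds its own eligibility and dose limits.

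The statistical stake is in Part B. DLT status and evaluability both depend on the share of M3814 received, and withdrawal stops that count where holding does not. Two participants with the same event could enter the dose-escalation model differently because their sites followed different sections.

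**Working it through.** **No power or sample-size figure is involved.** Section 9.1 states: "No formal statistical hypothesis will be tested, as the study is designed to be exploratory". The check sets the passages side by side and then counts doses.

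**Step 1: does any text remove the conflict?**

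- The bullet is limited to clinically significant events, but events managed under Table 15 and Section 6.9.2 can be clinically significant.
- The closing reference to Section 6.6.3 is joined by an or. It reads as adding triggers, not as importing that section's exceptions.
- Another Section 7.1 bullet withdraws for reactions that delay RT by more than 7 days (Part B). For the events in question it would be redundant if they already required withdrawal, so Section 7.1 itself seems to presume holding.
- Stopping M3814 alone is allowed, but it loses the same M3814 doses.
- Rechallenge under Section 7.1.1 points to Section 6.9, which describes holds and not a return after mandatory withdrawal.

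**Step 2: the Part B threshold.** Section 6.6.1 gives 8 of 10 doses: 0.80 × 10 = 8, reproduced. (The gloss in Section 6.6.3 of 2 days' treatment in Part B leaves 8/10 = 80%, which is not below 80%; it should be tidied too.)

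**Step 3: doses received.** M3814 is given on Days 1–5 and 8–12 (Table 2).

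| Withdrawn before the dose on | Doses received | Share |
|---|---|---|
| Day 8 | 5/10 | 50% |
| Day 9 | 6/10 | 60% |
| Day 10 (eighth dose) | 7/10 | 70% |
| Day 11 | 8/10 | 80% |

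Withdrawal before the eighth dose leaves less than 80%. From Day 11 onward the dose-loss route is closed.

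**Step 4: one event, two instructions.** Take in-field Grade 3 mucositis after fraction 6 (Day 8), otherwise meeting the evaluability criteria and the exemption.

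- Section 7.1: 6/10 = 60%, below 80%.
- Table 15, with recovery inside the 7-day allowance: up to 10/10, finishing by Day 12 + 7 = Day 19, within the 28-day DLT period. At least 8/10 makes the participant evaluable, with no DLT.

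**Step 5: how the 60% participant is classified.** Under the dose-loss bullet this is a DLT. If the exceptions override that bullet, it is not a DLT, and with fewer than 8 doses the participant leaves the Dose Escalation Analysis Set (Section 9.3).

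**Step 6: size in the model, as an illustration only.** Section 9.4.2 recommends only doses with P(DLT rate > 33%) < 25%. The trial's prior is not in the documents. As an assumption I use a one-dose beta-binomial, posterior Beta(a + x, b + n − x) for x DLTs in n, with four weak priors: Beta(1, 1), (0.5, 0.5), (0.25, 0.75) and (0.5, 1.5).

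| Data | P(DLT rate > 33%), range over the four priors |
|---|---|
| 0/3 (held and resumed) | 0.04–0.20 |
| 0/2 (withdrawn, not evaluable) | 0.07–0.30 |
| 1/3 (withdrawn, DLT) | 0.39–0.60 |
| 0/6 | 0.01–0.06 |
| 1/6 | 0.14–0.27 |

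Moving from 0/3 to 1/3 crosses 25% under all four priors. Moving from 0/3 to 0/2, or from 0/6 to 1/6, crosses it only under Beta(1, 1).

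**The case against.** Much can be said for the plan.

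- The exceptions in Section 6.6.3 follow the dose-loss bullet and are framed as exceptions to the definition above them. The natural reading is that they override it, so a withdrawn participant with an exempted event is not evaluable rather than a DLT. This stands as a likely reading, though the section does not say so expressly.
- The SMC confirms each DLT and may name others, so coding is not left to sites. This stands, but the SMC cannot restore doses that a withdrawal has removed.
- A related Grade ≥ 3 nonhematologic event outside the exceptions is a DLT however it is managed. This stands and confines the effect to exempted toxicities.
- Timing narrows it further. Appendix 8 puts acute esophagitis typically 2 weeks after treatment begins, after the last M3814 dose on Day 12 if there is no delay. It also says acute toxicities such as mucositis generally heal over weeks to months. If the delay exceeds 7 days, Table 15 generally stops M3814 as well, and both routes give the same dose count.
- Table 15 modifications are made by the investigator after discussion with the sponsor, which should reduce variation between sites.
- During the DLT and FE assessment periods of Parts A and FE, Section 6.9.1 itself refers to Section 7.1 for discontinuation and rules out dose reduction. Investigator-led interruption is introduced for the time afterwards, so the clash there lies mainly after those periods.

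A reader might infer that withdrawal turns an exempted event into a DLT, or that 1/3 can be set against a 33% overdose limit. The documents support neither. The first depends on a precedence that Section 6.6.3 leaves unstated. The second compares an observed proportion with a posterior-probability rule, and the SMC may depart from the model's recommendation.

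**Conclusion.** The contradiction is in the text, and the softening provisions do not resolve it. It covers Grade ≥ 3 nonhematologic and Grade ≥ 4 hematologic events against Table 15, Grade ≥ 3 SAEs and nonserious Grade 3 AEs against Section 6.9.1, Grade 3 only against Section 6.9.2, and esophagitis against Appendix 8.

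The consequence for the primary endpoint is conditional. It needs a Part B toxicity that Section 6.6.3 exempts, withdrawal before the eighth M3814 dose, and an alternative course in which recovery within 7 days lets the participant reach at least 8/10 doses. Then the passage followed separates an evaluable participant without a DLT from one who is either a DLT or not evaluable. The size in the model cannot be fixed without the trial's prior; the ranges above rest on assumed priors at a single dose. The case for correction does not depend on them, because a mandatory stopping rule should not contradict the management tables.

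**What to change.** Reconcile Sections 7.1 and 7.1.1 with Section 6.9.1, Table 15, Section 6.9.2 with Table 17, and Appendix 8, so that each event type and grade carries one instruction in each part. Grade ≥ 3 esophagitis should have a single instruction, with a statement of whether it belongs to the mucositis row of Table 15. Say how the closing reference to Section 6.6.3 in the Section 7.1 bullet is meant to work.

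In Section 6.6.3, state whether the exceptions override the criterion of less than 80% of M3814, and correct the days gloss beside it. Carry the same precedence into the definition of the DLT Analysis Set in SAP Section 8.2, so that a withdrawn participant with an exempted event is classified in one way only.

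Which clinical rule stands is for the sponsor to decide. The cost is amendment wording and a matching line in the SAP, with no added procedures, visits or participants.
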